2.6.5 Survival analysis

A Kaplan-Meier curve will summarise time to death by treatment group. Time to death is defined as randomisation to date of death, or last known alive. All APTS follow-up babies will be included in this analysis and censored at date of last follow-up. A cox regression will be used to obtain a hazard ratio for treatment, adjusted for gestational age.

2.6.6 Causes of death

Causes of death will be summarised by treatment.

Table 10: Primary causes of death for deaths by 24 months corrected age by treatment

	ICC	DCC
Primary cause of death	N (%)	N (%)
Total deaths		
Congenital abnormality		
Pulmonary hypoplasia		
Severe respiratory distress syndrome (RDS)		
Chronic lung disease		
Pneumonia		
Grade 3 / grade 4 IVH		
Meningitis		
Septicaemia		
Necrotising enterocolitis (NEC)		
Other		

2.7 Subgroups

The treatment effect for death or major disability at 24 months will be investigated in the following defined subgroups:

- Gender (Males vs. Females)
- Age: Infants of <27 weeks vs ≥27 weeks

This will be performed by fitting an interaction term between the subgroup of interest and treatment in a GEE model adjusted for multiple births. The two sided level of significance is 0.05. The relative risk for treatment will be determined from a model for each of the levels of the subgroup, e.g. a model for only females.

Page 13 of 17

Page 77 of 81

APTS FU Statistical Analysis Plan v2.2

Table 11: Subgroup analyses for the primary outcome of death or major disability at 24 months

Su	ubgroup	ICC	DCC	Relative risk (95% CI)	Interaction p-value
		n/N (%)	n/N (%)		
Gender	Males				
	Females				
Gestational Age	<27 weeks				
	≥27 weeks				

2.8 Bayley-III and ASQ-3 calibration sub-study

The aim in this sub-study is to validate the cut-offs provided by ASQ-3 developers in the APTS population. The APTS follow-up study was able to obtain funding for a sample of children to be assessed using the Bayley-III. In this sample of children, the Ages and Stages Questionnaire (ASQ-3) published cut-offs will be calibrated against the Bayley-III definitions of developmental delay.

A stratified sampling approach was taken in order to obtain a high risk sample of developmentally delay in order to calibrate these two instruments. Additionally, some sites routinely perform Bayley-III, and therefore we were also able to obtain an opportunistic sample of babies with a Bayley-III and matching ASQ.

Table 11 below maps the ASQ domains to the Bayley-III scores. Scatterplots, spearman correlations and ROC analyses may be used to compare these scores.

Table 12: Mapping of ASQ-3 domains to Bayley-III scores.

ASQ-3 domains	Bayley-III scores
Problem solving	Cognitive
Communication	Communication
Gross motor	Motor scale – gross motor
Fine motor	Motor scale – fine motor
Personal-social	Social emotional

August 2020

Page 14 of 17

Page 78 of 81

APTS FU Statistical Analysis Plan v2.2

Appendix One

Method to provide an estimate of the effect of the delayed cord clamping that might be achieved if the intervention was delivered according to the protocol.

Initially, the study sites will be grouped into **clusters** of (a) 50 or more infants based on geography and size of the neonatal unit or (b) of 10 or more infants. These clusters are shown in Table 9.

The primary measure of treatment adherence is the time in seconds to cord clamping $(\mu(\text{diff in sec}))$. For this measure, and for each cluster, the average difference between the two interventions in time to clamping (ΔTrAdh_i) is calculated:

 $\Delta \text{TrAdh}_i = \mu(\text{diff in sec})_i^{(DCC)} - \mu(\text{diff in sec})_i^{(ICC)} \quad \text{for } i = 1, \dots, 15$

The clusters will be ranked in order of increasing magnitude of this measure ($\Delta TrAdh_i$) and then grouped into 3 sets, low, medium and high adherence to treatment. For the primary measure, this will be by the difference in the average time to clamping between the interventions.

Within each of these three groups, using the same methods as for the analysis of the primary endpoint, a GEE model (logistic regression with a log-link) will be used to calculate the observed effect of delayed cord clamping on death and disability at 2 years to obtain RR_j , (*j*= 1 to 3) where RR_j is the relative risk for the *j*th group and the associated variance for the log of the estimate being $Var(ln(RR_j))$.

The weights for each of the low, medium and high groups (w_j) will be a weighted average of the Δ TrAdh_ivalues of the clusters within a group:

$$\frac{\sum_{i=1}^{5} n_i \times \Delta \operatorname{TrAdh}_i}{\sum_{i=1}^{5} n_i}, \quad \text{for } j = 1 \text{ (low)}$$
$$w_j = \frac{\sum_{i=6}^{11} n_i \times \Delta \operatorname{TrAdh}_i}{\sum_{i=6}^{11} n_i}, \quad \text{for } j = 2 \text{ (medium)}$$
$$\frac{\sum_{i=12}^{16} n_i \times \Delta \operatorname{TrAdh}_i}{\sum_{i=12}^{16} n_i}, \quad \text{for } j = 3 \text{ (high)}$$

August 2020

Page 15 of 17

Page 79 of 81

APTS FU Statistical Analysis Plan v2.2

where n_i is the number of babies within the i^{th} cluster.

A weighted analysis will be performed by multiplying the effect for each group by its weight and

dividing this quantity by the sum of the weights.

Thus, a weighted estimate (G) is given by

$$G = \ln(RR) = \frac{\sum_{j=1}^{3} w_j \times \ln(RR_j)}{\sum_{j=1}^{3} w_j}.$$

The variance (V) of this weighted quantity will be calculated as,

$$V = \operatorname{Var}(G) = \frac{\sum_{j=1}^{3} w_j^2 \times \operatorname{Var}(\ln(RR_j))}{(\sum_{j=1}^{3} w_j)^2}.$$

G is the log of the weighted estimate of the effect of delayed clamping on death and morbidity at 36 weeks, and $\exp(G)$ provides an estimate of the effect of the intervention, weighted by difference in the time to cord clamping (i.e. treatment adherence).

The 95% CI for this estimate can be calculated by using

 $\exp(G \pm 1.96 \times \sqrt{V}).$

August 2020

Page 16 of 17

Page 80 of 81

APTS FU Statistical Analysis Plan v2.2

References:

- 3. Donald B. Rubin (1996) Multiple Imputation after 18+ Years, Journal of the American Statistical Association, 91:434, 473-489, DOI: 10.1080/01621459.1996.10476908
- van Buuren, S., & Groothuis-Oudshoorn, K. (2011). mice: Multivariate Imputation by Chained Equations in R. *Journal of Statistical Software*, 45(3), 1 - 67. doi:http://dx.doi.org/10.18637/jss.v045.i03

August 2020

Page 17 of 17

Page 81 of 81

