2.6.3.1 Simple weighted approach

Firstly, an overall treatment adherence adjusted estimate will be calculated. This will be calculated using a simple weighting of the overall estimate of relative risk reduction (RRR):

 $RRR_{\text{adjusted}} = \frac{RRR}{100 - (\text{non compliance}^{(\text{ICC})} + \text{non compliance}^{(\text{DCC})})}$

Where

RRR is the relative risk reduction (%) for the primary outcome (Table 7) non compliance^(ICC) is the treatment non-adherence percentage for ICC in Table 3 non compliance^(DCC) is the treatment non-adherence percentage for DCC in Table 3

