2.6.3.2 Weighted subgroups by treatment adherence approach

Additionally, a weighted average approach, weighting by measures of treatment received will be undertaken, following the same principles used in the APTS main study analyses, while preserving the effect of randomisation. In these planned analyses we propose the following two approaches:

(a) sites which enrolled 50 or more babies will be considered a cluster and sites with less than 50 babies will be amalgamated to make a cluster of over 50 with other sites in the same geographic area;

(b) sites which enrolled 10 or more babies will be considered a cluster and amalgamated into a cluster with sites with less than 10 babies will be amalgamated with others in the same geographic area to form another 'cluster' with 10 or more babies (as shown in Table 9).

August 2020

Page 10 of 17

Page 74 of 81

APTS FU Statistical Analysis Plan v2.2

These clusters are slightly different from those proposed in the main paper as we have fewer patients with the follow-up component of APTS (1531 vs 1566), and also fewer with complete data at 2 years. Analysis (b), in which sites of 10 or more babies will be considered a 'cluster' as per Table 9, will allow us to assess the effect of placing less emphasis on the arbitrary grouping of sites by geographical location in analysis (a).

The main measure to be used to estimate treatment adherence will be the mean difference in clamp time (in seconds) between the ICC and DCC arms. Additional measures to be investigated include:

- mean clamp time in seconds in the DCC arm only
- proportion of compliant babies, where compliant is <10 seconds and not milked versus >=60 seconds and not milked
- proportion of babies who are compliant in the DCC arm only (>=60seconds and not milked)

For each measure of treatment adherence, the average for each treatment in each cluster will be calculated. For some measures, the difference between the two treatments will be calculated while for others, the measure of treatment received in the delayed clamping arm alone will be used. This value will then be used to rank the (a) 15 and (b) 22 clusters (as below in Table 9) for increasing adherence to protocol. These clusters in (a) and (b) will be grouped into 3 sets according to adherence to protocol, i.e. (a) 5 'low', 5 'medium' and 5 'good' adherence to protocol treatment (total 15 clusters) or (b) 7 'low', 8 'medium' and 7 'good' adherence to protocol treatment (total 22 clusters).

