The main measure to be used to estimate treatment adherence will be the mean difference in clamp time (in seconds) between the ICC and DCC arms. For example, if all babies in the control group complied with the protocol specifications we might expect an average clamp time to be 5 seconds, whereas in the delayed arm, the average time would be 60 seconds, so the achieved difference would be 55 seconds. The value of the treatment adherence to be used for that cluster would be 55.

For each measure of treatment adherence, a weighted analysis will be carried out to obtain an estimate of the effect of the intervention, weighted by the degree of treatment adherence. An estimate of the achieved effect of delayed cord clamping, for each of the 3 groups of clusters, will be obtained from a generalised linear model. A weighted average of the treatment adherence for each group will be calculated using a weighted average of the values for each cluster. Finally, an estimate of the effect of the intervention weighted for non-adherence will be derived by a weighted average of the 3 group estimates.

The details of the method are in Appendix One.

August 2020

Page 11 of 17

Page 75 of 81

APTS FU Statistical Analysis Plan v2.2

Table 9: Listing of sites within each cluster

25 APTS sites	15 clusters, obtained from individual sites with ≥50 patients or by amalgamating sites with <50 patients with others by geographic area	22 clusters, obtained from individual sites with ≥10 patients or by amalgamating 3 sites with <10 patients with others by geographic area
Aga Khan University	Pakistan	Pakistan
Hopital Antoine Beclere	France/N America	France
Fletcher Allen Health Care Medical Center Texas Children's Hospital IWK Health Centre		N America
Royal Jubilee Maternity Hospital Craigavon Area Hospital	Northern Ireland	Northern Ireland
Royal Hospital for Women	NSW and ACT	Royal Hospital for Women
Canberra Hospital		Canberra Hospital
Liverpool Hospital		Liverpool Hospital
Royal North Shore Hospital	RNS hospital	RNS hospital
Royal Prince Alfred Hospital	RPA hospital	RPA hospital
John Hunter Hospital	John Hunter	John Hunter
Mater Mothers Hospital	Queensland	Mater Mothers Hospital
Royal Brisbane and Women's Hospital		RBWH
Townsville Hospital		Townsville Hospital
Mercy Hospital For Women	Melbourne	Mercy Hospital For Women
Monash Medical Centre		Monash Medical Centre
Flinders Medical Centre	Flinders	Flinders Medical Centre
King Edward Memorial Hospital	KEMH	King Edward Memorial Hospital

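### The adherence-weighted estimator in SAP Appendix One averages three diluted relative risks and never scales to full adherence, so it does not estimate the on-protocol effect its heading promises; its summation limits and named endpoint also need correcting.

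*Supplement*

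**What the plan says.** SAP v2.2 plans two adherence analyses of the primary outcome in section 2.6.3, in addition to the primary GEE analysis by assigned treatment.

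- **Section 2.6.3.1 (simple approach)** divides the overall relative risk reduction by 100 minus the summed non-adherence percentages of the two arms. The input is defined thus: "RRR is the relative risk reduction (%) for the primary outcome (Table 7").
- **Section 2.6.3.2 and Appendix One (weighted approach)** rank site clusters by adherence, chiefly the mean difference in clamp time between arms, and form low, medium and high sets. In each set a GEE model "will be used to calculate the observed effect of delayed cord clamping on death and disability at 2 years". Section 2.6.3.2 then says that "an estimate of the effect of the intervention weighted for non-adherence will be derived by a weighted average of the 3 group estimates". Appendix One words this step as "A weighted analysis will be performed by multiplying the effect for each group by its weight and" then dividing by the sum of the weights, and gives the formula G = Σ w_j ln RR_j / Σ w_j, where w_j is the mean achieved clamp-time difference in set j.

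The heading of Appendix One states the purpose as "an estimate of the effect of the delayed cord clamping that might be achieved if the intervention was delivered according to the protocol". Section 2.6.3.2 mentions a 55-second contrast (60 s against 5 s) as an example of full compliance. That figure does not enter the formula.

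For option (a), section 2.6.3.2 specifies three sets of five clusters: "adherence to protocol treatment (total 15 clusters"). Option (b) has 22 clusters split 7, 8 and 7. The weight formula in Appendix One sums over clusters 1–5, 6–11 and 12–16. The closing text describes G as the log of the weighted estimate of the "effect of delayed clamping on death and morbidity at 36 weeks".

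**The concern.** An estimate of what deferred clamping would do if delivered as specified has to extrapolate from the contrast achieved to the contrast intended. Averaging the achieved effects, even with more weight on the better-adhering sites, stays inside the range of what was observed. If exp(G) is reported under the Appendix heading, a still-diluted relative risk will be read as the on-protocol effect. A reader who sees little movement from the intention-to-treat estimate could wrongly conclude that non-adherence mattered little.

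The index and endpoint slips are smaller, but they sit in the formula that a programmer would code from.

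**Working it through.** **1. Cluster count.** Table 9 lists 15 clusters for option (a): Pakistan; France/N America; Northern Ireland; NSW and ACT; RNS; RPA; John Hunter; Queensland; Melbourne; Flinders; KEMH; NZ; Auckland; Christchurch; Wellington. It lists 22 for option (b). Both counts agree with section 2.6.3.2, and Appendix One defines the adherence measure for i = 1 to 15. The printed sums, however, give 5 + 6 + 5 = 16. Cluster 16 does not exist, and read literally cluster 11 moves from the high set to the medium set. No limits are printed for option (b).

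**2. Endpoint.** The group models use death and disability at 2 years, and section 2.5 defines the primary outcome as death and/or major disability at 24 months. The closing sentence of Appendix One names a 36-week outcome instead.

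**3. The plan's own view of dilution.** SAP Table 1 gives 80% power for 35% to 25% with N = 1350 and 30% non-compliance. Shrinking the difference to 0.10 × 0.70 = 0.07 and using the normal approximation for two proportions gives power 0.791. The six rows give 0.786 to 0.793. So the SAP itself treats the observed effect as a reduced version of the on-protocol effect.

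**4. Bound on G (no dilution assumption needed).** With all w_j > 0, G is a convex combination of ln RR_1, ln RR_2 and ln RR_3. Hence exp(G) cannot pass the most extreme group RR. If w_1 = w_2 = w_3, the weights cancel and G is the plain mean.

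**5. Size under assumed contrasts.** Assume ln RR_j = ln RR_full × w_j/55. Then G / ln RR_full = (Σw² / Σw) / 55. The group contrasts below are assumptions.

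| Group contrasts (s) | Σw²/Σw (s) | Share of full log effect |
|---|---|---|
| 20, 40, 54 | 4916/114 = 43.1 | 0.784 |
| 25, 40, 52 | 4929/117 = 42.1 | 0.766 |
| 30, 40, 50 | 5000/120 = 41.7 | 0.758 |
| 20, 35, 50 | 4125/105 = 39.3 | 0.714 |
| 38.5 in all three | 38.5 | 0.700 |
| 55 in all three | 55 | 1.000 |

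If dilution is instead proportional on the RRR scale, the last four rows give 0.729, 0.687, 0.663 and 1.000 for RR_full = 0.714. Short of full adherence, the cases tried therefore span about 66% to 78%.

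As relative risks:
- RR_full = 25/35 = 0.714 with 30/40/50 s: group RRs 0.832, 0.783 and 0.737; plain average 0.783; exp(G) = 0.775.
- RR_full = 0.714 with 38.5 s throughout: exp(G) = 0.790, the same as the unadjusted value.
- RR_full = 0.80 with 25/40/52 s: plain average 0.80^(39/55) = 0.854; exp(G) = 0.80^0.766 = 0.843.

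**6. Scaling instead of averaging.** Taking equal variances, the slope through the origin b = Σ w_j ln RR_j / Σ w_j², multiplied by 55, returns 0.714 in the 30/40/50 s case. It returns 0.723 if dilution is linear in RRR.

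**7. Units in section 2.6.3.1.** With RRR = 20 and total non-adherence of 30, the formula gives 20/70 = 0.286. This is a fraction, although RRR is entered in percent; multiplied by 100 it is 28.6%.

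**The case against.** - **Supplementary status.** This analysis does not alter the primary comparison. That stands, and it limits the severity.
- **Modest wording elsewhere.** Section 2.6.3.2 calls the result a weighted average, and the end of Appendix One calls it weighted by difference in time to clamping. Both are accurate. Only the heading overclaims, so relabelling is an acceptable remedy.
- **Clerical slips.** The rest of the SAP fixes the intended grouping (5/5/5 and 7/8/7) and the intended endpoint, so a careful programmer would recover them. That is fair, but the formula as printed is still wrong.
- **Precision.** G ignores the variance of each group RR in its weights. This costs efficiency, not validity, because the stated variance formula propagates correctly for the chosen weights.
- **The 55 s figure.** It is an illustration, and the intervention is defined as 60 seconds or more. The documents therefore fix no unique full contrast, and one must be declared.

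Two stronger readings are tempting, and the documents do not support them. First, a reader might infer that the simple formula necessarily overstates the effect, because a baby clamped just outside its window counts as fully non-adherent. In the 25/40/52 s example the diluted RRR is 14.6%, and 14.6/0.70 = 20.9% against an assumed truth of 20%, so there it nearly recovers the target. Second, a reader might infer from the follow-up grant application (section 4.2, Table 2: median clamp times 5 s and 60 s) that the full contrast was achieved. Those are medians in 488 infants at November 2012, with ranges 0–58 s and 0–80 s. The SAP measures adherence by the difference in means, and a median of 60 s is compatible with substantial non-adherence in the deferred arm.

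**Conclusion.** Wrong as written, of moderate severity, and confined to a supplementary analysis. The estimator in Appendix One cannot target the on-protocol effect unless every adherence group is already fully adherent or the effect is null. That conclusion follows from the algebra and needs no dilution model; it concerns what is being estimated, since sampling noise can move any single result.

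The size, roughly 66% to 78% of the full log effect, is illustrative. It rests on assumed group clamp times, proportional dilution and 55 s as the full contrast. The mismatch of summation limits and the wrong endpoint are certain from the text.

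It does not follow that the SAP has no analysis that scales to full adherence: section 2.6.3.1 does scale, under an all-or-none assumption that should be stated.

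**What to change.** 1. **Estimator.** For the clamp-time difference measure, report exp(c·b) with its 95% CI over the three adherence groups, where b = Σ(w_j ln RR_j / V_j) / Σ(w_j² / V_j), Var(b) = 1 / Σ(w_j² / V_j) and V_j = Var(ln RR_j). State c in advance, for example the SAP's illustrative 55 s. For the measure based on compliant babies c would be 100%, with compliance expressed so that zero means no contrast between arms, as in the denominator of section 2.6.3.1. State the assumption of linearity through the origin.
   - *Alternative:* keep G, drop the on-protocol wording from the heading, and describe exp(G) only as an adherence-weighted average.
2. **Level of fitting.** Stay with three groups. Option (b) allows clusters of 10 babies; with 5 per arm and a 35% event rate, the chance of no events in an arm is 0.65^5 ≈ 12%, which leaves ln RR undefined.
3. **Limits.** Use 1–5, 6–10 and 11–15, and add 1–7, 8–15 and 16–22 for the 22-cluster version.
4. **Endpoint.** Change the closing sentence of Appendix One to death or major disability at 24 months.
5. **Section 2.6.3.1.** Keep it, multiply by 100 so that it returns a percentage, and label its all-or-none adherence assumption.

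The cost is a few lines of SAP text and short code. The scaled estimate will have a wider interval and depends openly on the linearity assumption.
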